6.3 Adverse events and unanticipated problems

Oversight:

Oversight of the pilot will be the responsibility of Drs. [name] and [name], the Principal Investigators.

The co-leads and study investigators will meet on a regular basis throughout the study period and will be in direct contact with clinical leadership involved in the project to obtain ongoing feedback. In addition, the protocol will be overseen by the Institutional Review Board (IRB).

De-identified study data will be accessible at all times for the BWH PI and coinvestigators to review during the conduct of the trial and during the study analysis, if applicable. We will also ensure that all protocol deviations for the pilot study are reported to the NIH and the IRB according to the applicable regulatory requirements. Compliance of regulatory documents and study data accuracy and completeness will be maintained through an internal study team quality assurance process.

Definition:

Adverse Event (AE): Any untoward or unfavorable medical occurrence in a human study participant, including any abnormal sign (e.g. abnormal physical exam or laboratory finding), symptom, or disease, temporally associated with the participants' involvement in the research, whether or not considered related to participation in the research.

- Adverse Events will be classified using the following rating scales:
 - o Severity: Mild, Moderate or Severe
 - Mild: Awareness of signs or symptoms but are easily tolerated
 - Moderate: Events introduce a low level of inconvenience or concern but may interfere with daily activities but are usually improved by simple therapeutic measures.
 - Severe: Events interrupt the participants' normal daily activities and generally require systemic drug therapy
 - o Expectedness: Unexpected or Expected
 - Unexpected: nature or severity of the event is not consistent with the condition under study
 - Expected: event is known to be associated with the intervention or condition under study.

Serious Adverse Event (SAE): Any adverse event that:

- Results in death
- Is life threatening, or places the participant at immediate risk of death from the event as it occurred

- Requires or prolongs hospitalization
- Causes persistent or significant disability or incapacity
- Results in congenital anomalies or birth defects
- Is another condition which investigators judge to represent significant hazards

Determination:

Given the minimal risk nature of the study where the overall goal is to improve patient safety, the intervention is a quality improvement intervention, all prescribing decisions are made by providers who will provide consent, we do not anticipate any SAEs or AEs.

Reporting:

No SAEs or AEs are expected as part of this study, which aims to increase patient safety through the avoidance of high-risk medications. The study team will not be providing any direct care to patients and all treatment decisions will ultimately be made by the patients' medical teams at Brigham and Women's Hospital. While we will not be actively monitoring the occurrence of adverse events, which if done would require direct patient contact, detailed patient-level chart-reviews, and clinical assessments conducted by the study team, we anticipate that the study team will be informed of any AEs or SAEs that do occur through hospital safety reports.

If we become aware of any AEs or SAEs throughout the course of the study, we will collect this information. Any reports of deaths will be submitted to the NIA Program Officer and to the Safety Officer (SO) within 24 hours. Any unexpected SAEs will be reported to the NIA PO, SO and the IRB within 48 hours of the study's knowledge of the SAE. All other reported SAEs and AEs received by the study team will be reported to the NIA Program Officer and to the SO quarterly, unless otherwise requested by the Safety Officer or Roybal Center Program Data Safety Monitoring Board (DSMB).

7. Statistical Considerations

7.1 Statistical Hypotheses

Our null hypothesis will be that number of high-risk medication doses prescribed per day to eligible patients assigned to intervention providers will be no different than those in the control arm.

7.2 Sample size determination

As described in Section 4.3, we expect at least 36 interns to participate in the trial (18 per arm), and that at least 430 patients will be eligible for inclusion in the analysis, with approximately 3 eligible days per patient (i.e., 1290 patient-days of observations). With these estimates, we would have >80% power to detect a mean difference of 0.5 high-risk medication doses per patient-day in the intervention arm compared with the control arm, assuming a standard deviation of 1.1, power=0.8, alpha of 0.05 (two-sided), and patient correlation of 0.2, a conservative estimate.^{13,35} We also assumed an average cluster size of 12 patients (and 36 patient-days) per provider based on preliminary estimates. As these data are intended to provide pilot data for larger evaluations, any positive signal from this pilot trial will help inform next steps.

7.3 Statistical analyses

7.3.1 *Analysis of the primary endpoint*

The unit of analysis is at the patient-level. We will evaluate the primary outcome using generalized estimating equations to adjust for physician-level clustering and multiple patient-day observations per physician using a log-link function, Poisson-distributed errors, and fixed effects for the treatment group and month of the year to account for seasonality. This approach will account for correlations between repeated measurements. Because this is a randomized trial, our primary analyses are planned as unadjusted; however, if there are strong predictors of the outcomes not balanced by stratified randomization, we will adjust for these in the primary analyses. We will conduct analyses using intention-to-treat principles. Given the nature of the data and how the outcomes are measured in EHR data, there will not be missing data for the primary outcome.

7.3.2 *Analysis of secondary endpoints*

We will use a similar approach for the secondary outcomes. For discharge medication orders (secondary outcome), we will also use generalized estimating equations that adjust for physician-level and patient-level clustering using a logit-link function, binary-distributed errors, and fixed effects for the treatment group and month of the year. For the outcomes measuring spillover

effects, the approach will be the same, except using a log-link function and Poisson-distributed errors. Given the nature of the data and how these outcomes are being measured primarily in EHR data, there should not be missing values. Because this is a randomized trial, our primary analyses are planned as unadjusted; however, if there are strong predictors of the outcomes not balanced by randomization, we will adjust for these in the primary analyses.

The implementation outcomes will be measured at the provider-level. The characteristics of consenting and non-consenting physicians will be measured descriptively, comparing the values using t-tests and chi-square tests or non-parametric analogs, as appropriate. Other implementation outcomes will be measured descriptively.

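### Section 7.3.1 fixes no small-sample inference method for a GEE on at least 36 interns; an uncorrected sandwich with a normal reference would give about 8-13% false positives with categorical months, not 5%

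*Combined protocol and SAP*

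**What the plan says.** Section 7.3.1 uses "generalized estimating equations to adjust for physician-level clustering and multiple patient-day observations per physician using a log-link function, Poisson-distributed errors" with "fixed effects for the treatment group and month of the year to account for seasonality". It allows further covariates if strong predictors turn out unbalanced. For discharge orders, Section 7.3.2 says "we will also use generalized estimating equations that adjust for physician-level and patient-level clustering using a logit-link function"; the spillover outcomes use the Poisson form again.

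Section 7.2 states "we expect at least 36 interns to participate in the trial (18 per arm"), "alpha of 0.05 (two-sided") and "we would have >80% power to detect a mean difference of 0.5 high-risk medication doses per patient-day". Section 3.2 makes the intern the unit of randomisation and describes two-week service blocks. Section 4.3 gives a 6-month recruitment window, at least 96 eligible interns and uptake of at least 40%. Section 5.3 stratifies randomisation by three services.

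No section names a working correlation, a variance estimator, a small-sample correction, a reference distribution or degrees of freedom, or says whether month is categorical.

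**The concern.** The ordinary GEE sandwich variance is justified for a large number of clusters. It is biased downwards when clusters are few relative to the parameters fitted. With six categorical months the model has an intercept, a treatment term and five month terms: 7 parameters on 36 interns. Any added covariates make this worse.

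The intervals would then be too narrow, and the test would exceed the stated two-sided 5%. Section 7.2 says "any positive signal from this pilot trial will help inform next steps", so the apparent strength of that signal is what is at stake. The choice of variance method also decides whether the power claim stands.

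**Working it through.** **1. The plan's power figure.** Inputs from Section 7.2: difference 0.5, SD 1.1, correlation 0.2, 18 interns per arm, and "We also assumed an average cluster size of 12 patients (and 36 patient-days) per provider based on preliminary estimates".

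- Design effect: 1 + (36 - 1) x 0.2 = 8.
- Patient-days per arm: 18 x 36 = 648; effective number 648 / 8 = 81.
- SE = 1.1 x sqrt(2/81) = 0.173; 0.5 / 0.173 = 2.89.
- Power: 82.5% with z, 80.2% with t on 34 df, 79.8% with t on 36 - 7 = 29 df.

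The stated figure is reproduced with z, and the margin is almost nil.

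**2. False-positive rate under the null.** From the plan: 36 interns (also 38, since 0.40 x 96 = 38.4), 12 patients x 3 days each, SD 1.1, correlation 0.2. Assumed: mean 0.5, 0.75 or 1.0 doses per day; cluster-size CV 0 or 0.4; a second correlation of 0.05; 48 interns as a larger case. The model has gamma intern and patient effects with Poisson patient-days, analysed by log-link Poisson GEE under independence and exchangeable working correlation. There were 4,000 runs per setting (Monte Carlo error about +/-1 point at 10%), or 1,500 for the straddling-block case.

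A 0.5-dose reduction needs a control mean of at least 0.5, hence the lower bound. At mean 1.0 and correlation 0.2 the SD cannot be exactly 1.1: Poisson variance 1.0 plus intern variance 0.2 x 1.21 = 0.242 gives SD 1.114, a small departure.

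| Month handling and interns | Ordinary sandwich, z |
|---|---|
| Categorical, 36 interns | 9.9-13.1% |
| Categorical, 38 interns | 8.7-12.6% |
| Categorical, 48 interns | 7.8-10.6% |
| Categorical, two-week blocks straddling months, 36 interns | 8.2-11.4% |
| Linear month term | 7.0-9.4% |
| No month term | 6.3-8.8% |

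A second simulation, stratified by service and with cluster-size CV about 0.5, gave 9.2-13.1% at 36 interns with categorical months. A standard-package run on patient-day rows (mean 0.75, correlation 0.2, exchangeable, 4,176 runs) gave 10.5%.

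**3. Alternatives, categorical months.**

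- Ordinary sandwich with t on 29 df: about 8-12%.
- Model-based variance with z: 6.3-9.6% or 9.2-14.1%, depending on how scale and correlation are estimated.
- Mancl-DeRouen with z, 36-38 interns: 3.6-5.1% (4.8-7.2% without month terms); 4.2% in the standard-package run.
- Kauermann-Carroll with t on interns minus parameters: 5.1-7.5%.

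For the logit discharge model (assumed prevalence 10-30%, correlation 0.02-0.2), the ordinary sandwich gave 9.0-10.2% and Mancl-DeRouen with z 3.0-4.4%.

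**4. Power under each method.** 1.0 versus 0.5 doses per day, 36 interns, correlation 0.2, 6,000 runs:

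| Method | SD 1.1 in both arms | Variance proportional to mean |
|---|---|---|
| Ordinary sandwich, z | 74.6-74.8% | 88.8-90.6% |
| Ordinary, critical value reset to a true 5% | 56.7-64.7% | 77.1-83.0% |
| Mancl-DeRouen, z | 58.1-62.3% | 75.6-80.2% |
| Kauermann-Carroll, t | 64.7-66.8% | 81.4-84.7% |

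The reset critical values were 2.37-2.59 instead of 1.96.

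**5. Sparse months.** If month is constant within an intern and only one intern falls in a month, that intern alone fits the month effect (leverage 1) and Mancl-DeRouen is undefined. With random uptake this arose in 191 of 3,000 simulated trials (6.4%); with assumed skewed uptake of 5-25% per month, in 37-40%. Straddling blocks would make it rarer.

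**The case against.** The strongest reply is that the plan is silent rather than wrong: an analyst using a corrected estimator would comply fully with 7.3.1. That stands, and it makes every inflated rate above conditional.

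Two stronger readings are tempting. One is that the plan ignores clustering; it does not, because it clusters on physician. The other is that the primary test has a 9-13% error rate. The documents do not commit to the uncorrected sandwich, and that range belongs to interns spread evenly over six categorical months at or near the minimum of 36. Straddling blocks, 38 interns or fewer month parameters bring it down.

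It is also fair that the dose rates are assumed, and that Section 7.2 speaks of a patient correlation, which is applied here at intern level. The excess nevertheless appears at every mean from 0.5 to 1.0 and at correlations of both 0.05 and 0.2.

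Lastly, this is a pilot meant to inform larger evaluations, with no p-value rule for proceeding. That limits the consequence. It does not remove the gap, because the plan states a null hypothesis, an alpha and a power.

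**Conclusion.** The gap holds in conditional form. With at least 36 interns and about 7 parameters, the unspecified variance method moves the false-positive rate from about 4-5% (Mancl-DeRouen with z) to about 8-13% (ordinary sandwich with z) when months are categorical. With a linear month term or none, the ordinary sandwich gives about 6-9%. A t reference alone is not a cure.

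These rates rest on assumed means of 0.5-1.0 doses per day, SD 1.1 and intern-level correlations of 0.05-0.2. Much of the excess comes from the month terms, and it shrinks as more interns enrol. The stated alpha, the confidence intervals and the weight given to a positive result are affected. It should be fixed; confidence in the size is medium.

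**What to change.** In 7.3.1, before unblinding, prespecify one of:

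- the Mancl-DeRouen sandwich clustered on intern, with a normal reference (about 4-5% with categorical months, about 5-7% without month terms);
- Kauermann-Carroll with t on interns minus parameters (about 5-7.5%, slightly liberal);
- a randomisation test respecting the service strata (acceptable in principle; not simulated here).

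State the working correlation and how month enters. Pool adjacent months, or use a coarser season term, when a month has only one or very few interns. Apply the same rule to the GEEs in 7.3.2.

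Restate the power in 7.2 under the chosen method. The sponsor should see the drop plainly: with Mancl-DeRouen, about 58-62% if the SD is equal in both arms, or 76-80% if variance is proportional to the mean, against the claimed >80%. Most of that drop is removal of invalid rejections; compared with the ordinary sandwich held to a true 5%, the loss is at most about 3 points.

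The drafting cost is a few sentences and an option available in standard software. No design feature or data collection changes.

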BWH and BWFH uses 2-week service blocks for its inpatient general medicine evening coverage, and the service overall consists of 6 day and 8 evening (twilight) teams covering geographically distinct wards at 2 hospital sites with daily censuses of 15-20 patients. These teams typically consist of an attending, a resident, an intern (i.e., 1st year of residency), and medical students. There is no cross-coverage across teams. We will focus on interns from the “twilight” (i.e., evening) teams as they cover the shifts during which the high-risk medications of interest (specifically anti-psychotics, benzodiazepines, and sedative hypnotic “Z-drugs”) are typically first initiated and are also the first point of contact for nurses, pharmacists, and other physicians. Given their stage of training and the nature of their workflow, they are also most prone to make decisions using System 1 thinking.

At the beginning of each rotation, we will identify the interns assigned to the twilight teams (i.e., the primary prescriber and responding clinician on the general medicine service team). We will invite these interns to participate in the study via email invitation. Interns who consent will be randomized in a 1:1 ratio with a random number generator to one of 2 arms: (a) Arm 1: simulation intervention and (b) Arm 2: control (online education) intervention. The unit of randomization will therefore be the intern. Randomizing at the intern level will reduce the possibility of contamination across patients. Providers will receive \$25 for completing the initial provider survey, \$75 for completing the intervention or control assignment (e.g., simulation or online education training), and \$50 for completing the endline (follow-up) questionnaire. Other ward staff will be blinded to arm assignment to the extent possible. Data analysts will be blinded to arm assignment. This is a highly feasible approach used by investigators conducting provider-facing intervention trials at BWH.

[figure not shown]

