5.3 Measures to minimize bias: randomization and blinding

Interns who consent will be randomized in a 1:1 ratio to receive either intervention or control using a random number generator. We plan to conduct stratified randomization based on the service to which the intern is assigned to (GMS, ITU, or Faulkner).

The providers will not be blinded to which arm to which they were assigned, as blinding in the context of an intervention that is intended to motivate action will be infeasible. Physicians randomized to control will not have any way of accessing the intervention. Of note, once on a twilight team, interns are unlikely to rotate back onto a service, so contamination across arms should be minimal. Either way, if this does happen, they will not be re-randomized in the trial. Other ward staff and analysts will be blinded to arm assignment to the extent possible.

6. Study Assessments and Procedures

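### Service (GMS, ITU, Faulkner) stratifies the randomisation but is left out of the primary, discharge and spillover models; pre-specifying it would recover precision if prescribing differs by service

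*Combined protocol and SAP*

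**What the plan says.** Section 5.3 makes service the stratification factor: "We plan to conduct stratified randomization based on the service to which the intern is assigned to (GMS, ITU, or Faulkner"). The only allocation mechanism described is this: "Interns who consent will be randomized in a 1:1 ratio to receive either intervention or control using a random number generator". Neither blocks nor any other device for keeping the arms level within a service is mentioned.

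Section 7.3.1 specifies a Poisson GEE with a log link, clustered on physician, with "fixed effects for the treatment group and month of the year to account for seasonality". Section 7.3.2 specifies the discharge-order model with a "logit-link function, binary-distributed errors, and fixed effects for the treatment group and month of the year". For the spillover outcomes it says of their "effects, the approach will be the same, except using a log-link function and Poisson-distributed errors". Service is not a covariate in any of the three.

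The main analyses are described as unadjusted, with one exception: "if there are strong predictors of the outcomes not balanced by stratified randomization, we will adjust for these in the primary analyses". Section 7.3.2 repeats this in nearly the same terms. The closest the plan otherwise comes to service is the exploratory look at differences between teams in Section 7.3.4. That concerns effect modification and does not alter the main models.

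**The concern.** A factor is usually chosen for stratification because it is expected to predict the outcome. The plan gives grounds for that expectation: Section 3.2 describes "8 evening (twilight) teams covering geographically distinct wards at 2 hospital sites", and Section 6.1 expects characteristics of the team to affect outcomes even after randomisation. Yet the analysis ignores the factor.

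The fallback clause does not close the gap. If stratification works, service is balanced and never qualifies for adjustment. If it does not work, inclusion is decided after the data are seen, with no threshold for what counts as a strong predictor or as imbalance.

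With 36 interns, between-intern variance dominates the standard error, so any part of it explained by service is worth removing. A second effect depends on the allocation method. If balance is enforced within service and the standard error is otherwise valid, a model without service overstates the standard error, because it charges the treatment contrast with variation that the design has already removed. Under simple allocation there is no such mismatch, only lost power.

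**Working it through.** **Inputs from Section 7.2.** SD 1.1 (variance 1.21), correlation 0.2, 18 interns per arm, difference 0.5 doses per patient-day, two-sided alpha 0.05, and 12 patients or 36 patient-days per intern.

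**Assumed input.** Let f be the share of between-intern variance due to service. The documents give no value; 0, 10, 25 and 40% are used.

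**The plan's own figure.** The variance of an intern mean is 1.21 × (0.2 + 0.8/m), and SE = √(2 × variance/18).

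- m = 36: variance 0.269, SE 0.173, power about 82%. This reproduces the stated power of more than 80%.
- m = 12: variance 0.323, SE 0.189, power about 75%.

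The between-intern part of that variance is 0.2/(0.2 + 0.8/12) = 75% at m = 12 and 0.2/(0.2 + 0.8/36) = 90% at m = 36.

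**With service in the model.** The variance becomes 1.21 × (0.2(1 − f) + 0.8/m). At m = 12 the SE is 0.189, 0.182, 0.171 and 0.158 for the four values of f.

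**Power when balance is enforced within service** (normal approximation):

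- without service: 1 − Φ((1.96 × SE_without − 0.5)/SE_with)
- with service: 1 − Φ(1.96 − 0.5/SE_with)

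| f | m = 12: without / with | gain (points) | SE overstated without service, m = 12 | m = 36: without / with | gain (points) |
|---|---|---|---|---|---|
| 0% | 75 / 75% | 0 | 0% | 82 / 82% | 0 |
| 10% | 76 / 78% | 2.4 | 4% | 84 / 86% | 2.2 |
| 25% | 77 / 83% | 5.9 | 11% | 86 / 91% | 5.2 |
| 40% | 79 / 88% | 9.2 | 20% | 88 / 95% | 7.3 |

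Gains are taken before rounding. The overstatement is SE_without/SE_with − 1; at f = 40%, 0.189/0.158 gives about 20%.

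**Simulation with month terms.** There were 36 intern means at m = 12, three services of 12 interns and six months (both layouts assumed), no true month effect, and five month terms in every model. Allocation was either 6:6 within each service or unrestricted within service. Each setting had 8,000 runs (Monte Carlo error about 0.5 points). The test used a leverage-corrected robust SE (HC2) with a t reference on residual degrees of freedom.

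| f | change in power from adding service, balance enforced | same, simple allocation |
|---|---|---|
| 0% | −0.2 | −3.4 |
| 10% | +2.8 | +0.6 |
| 25% | +9.3 | +7.2 |
| 40% | +15.7 | +14.6 |

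These gains at f = 25 and 40% exceed the formula's, and they depend on how months fall across services. With other month layouts the 40% gain under enforced balance came out near 12 points. The direction was the same throughout.

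**Type I error in the same simulation.**

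- Uncorrected sandwich SE with a z test, without service: 9.6, 8.2, 6.4 and 4.3% across f under enforced balance; 9.4 to 10.0% under simple allocation.
- Uncorrected sandwich SE with a z test, with service: 10.9 to 12.3%.
- Corrected SE with a t test, with service: 5.0 to 5.9%.

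Adding the service term alone therefore moves an uncorrected test further from 5%. The term and the correction belong together.

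**Scale.** All figures use the mean-difference scale of Section 7.2, because the documents give no control-arm dose rate from which to simulate the planned Poisson model. Nothing was computed for the discharge or spillover outcomes.

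**The case against.** The strongest opposing case is that nothing here is invalid. The estimate is unbiased, the plan openly chooses an unadjusted analysis, and this is a pilot. The documents give no between-service difference, so even the sign of the benefit is unknown: under simple allocation the change is −3.4 points if service is irrelevant and only +0.6 at 10%. All of that stands, and it is why this is an efficiency recommendation and no more. It does not remove the case for the change, because the possible loss is small and the possible gain is several times larger. Nor is the unadjusted label a reason of principle, since month is already a pre-specified covariate.

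The overstated SE is also conditional. It needs enforced balance, which Section 5.3 does not state, and an otherwise valid SE. With an uncorrected sandwich SE, type I error exceeds 5% in most settings, so the few-cluster problem outweighs it. That is correct.

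It can further be said that the small-sample correction is a separate matter with its own cost: without service, moving from the uncorrected z test to the corrected t test lowered the rejection rate at a difference of 0.5 from about 76% to 66%. The correction is needed with or without service, and Section 7.3 does not state the SE method. But the higher rate comes from a test running near 10% type I error, so the drop is not a loss of real power.

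Finally, in the logit discharge model a service term makes the odds ratio conditional on service. That stands, and the plan should say so.

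**Conclusion.** The concern holds. Service defines the randomisation strata and is absent from all three models, and the fallback clause would not bring in a stratum that balanced as intended. The consequence is lost precision, with an over-wide SE as well if balance is enforced within service and the SE is otherwise valid. It is not bias.

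At 12 patients per intern with balance enforced, the formula puts the gain at 2.4 to 9.2 points of power when service carries 10 to 40% of between-intern variance. The simulation puts it at about 3 to 16 points under enforced balance and 1 to 15 under simple allocation. If service does not predict prescribing, the change costs about 0 to 3 points.

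The sizes rest on the assumed values of f, equal numbers of interns per service, six months of recruitment, and the linear scale. Confidence in the direction, given that service matters, is high; confidence in the size is moderate at best.

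**What to change.** - **Section 7.3.1:** name service (GMS, ITU, Faulkner) as a fixed effect alongside treatment and month, included whatever the observed balance.
- **Section 7.3.1:** specify a small-sample corrected robust SE, for example Kauermann-Carroll, and a t reference with intern-level degrees of freedom.
- **Section 7.3.2:** carry both into the discharge and spillover models, and state that the discharge odds ratio is then conditional on service.
- **Section 5.3:** add one clause saying whether balance is enforced within service, and how.

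No new data are needed, since service is known at randomisation. The cost is two degrees of freedom. With 36 interns and six months, residual degrees of freedom are 36 − 1 (intercept) − 1 (treatment) − 5 (months) = 29, falling to 27 with service. To this is added the small power loss given above if service turns out not to matter.
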